#### **6.2.10 NYHA Class**

Frequencies of patients in the different NYHA classes will be presented by treatment group and overall by visit.

Frequencies of patients with change in NYHA class from baseline (e.g. unchanged, improved by 1 category, deteriorated by 1 category, etc.) will be presented by treatment group and visit.

The number of patients with transitions from baseline with respect to categories (class I, class II, class III, class IV) will be provided by baseline value, treatment group and visit.

#### **6.2.11 PGIC and PGIS**

Frequencies of patients in the different PGIC/S categories will be presented by treatment group and overall by visit.

Frequencies of patients with change in PGIC/S class from baseline (e.g. unchanged, improved by x categories, deteriorated by x categories, etc.) will be presented by treatment group and visit.

### **6.3 Safety**

Safety analyses will be performed in the SAF.

#### **6.3.1 Adverse events**

Adverse events (AEs) will be coded using MedDRA terminology. The version number of MedDRA used for the analyses will be stored in the clinical database. A listing will be provided linking the original investigator terms and the coded terms.

AEs are considered to be treatment-emergent if they have started or worsened after first application of study medication up to 5 calendar days after end of treatment with study medication.

An overall summary of AEs and treatment-emergent (TE) AEs will be generated by treatment group and overall.

Incidences of patients with TEAEs, drug-related and/or serious TEAEs, TEAEs causing discontinuation of study treatment will be summarized by treatment group and overall

grouped by MedDRA Primary System Organ Class (SOC) and Preferred Term (PT). In addition, the incidence of pre-treatment AEs and AEs during the follow-up (more than 5 calendar days after end of treatment with study medication) will be tabulated. Serious adverse events (SAEs), deaths, and AEs leading to discontinuation will be listed. The date, relative day (to study medication) and phase of the study (pre-treatment, during treatment, post-treatment) will be included.

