If permanent discontinuation of study drug treatment becomes necessary due to intolerance even at the lowest dose step or any other reason, this does not mean that the patient has withdrawn from the study follow-up. Participants may be allowed to begin study treatment again if deemed medically appropriate, unless the participant's treatment assignment has been unblinded by the investigator/delegate and/or non-study treating physician.

For participants who are discontinued from study treatment but continue to be monitored in the study, all visits and procedures, as outlined in the schedule of assessments, should be completed. If the patient is unable to attend scheduled study visits, follow-up of clinical events specified as exploratory endpoints may continue by phone, unless the patient explicitly withdraws his/her consent to any type of follow-up.

Withdrawal criteria

Patients *must* be withdrawn from the **study drug**, while all efforts should be made to continue all protocol procedures also upon study drug discontinuation, if any of the following occurs:

- In case of pregnancy or breastfeeding.
- If the investigator believes that for safety reasons (i.e., adverse event) it is in the best interest of the subject to stop study drug even at the lowest dose.

Patients *may* be withdrawn from the **study drug** if any of the following occurs:

- If a significant violation of the protocol occurs, as defined by the sponsor and the coordinating investigator.
- If the randomization code is broken via IxRS.

Patients *must* be withdrawn from the **study** if any of the following occurs:

- At their own request; at any time during the study and without giving reasons, a patient may decline to participate further. The patient will not suffer any disadvantage as a result.

Patients *may* be withdrawn from the **study** if any of the following occurs:

- If, in the investigator's opinion, continuation of the study would be harmful to the patient's well-being.
- At the specific request of the sponsor and in liaison with the investigator (e.g., obvious non-compliance, safety concerns).

Depending on the time point of withdrawal, a withdrawn patient is referred to as either "screening failure" or "dropout" as specified below:

Screening failure

A patient who, for any reason (e.g. failure to satisfy the selection criteria), terminates the study before the time point used for the definition of "dropout" (see below) is regarded a "screening failure".

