9.2.8 Visit 8 – Day 126±3 (Week 18)

Patients need to come for this visit without taking the morning dose of the study drug (this applies only for the study drug. All others medications shall be taken as scheduled)

- KCCQ, EQ-5D-5L, PGIC/S (see Section [9.4](#))
- Assessment of NYHA class
- Concomitant medications (see Section [8.1](#))
- Adverse events (see Section [9.6.1](#))
- Physical examination
- Vital signs in sitting position (BP and pulse rate). See Section [9.7.5](#)
- Drug accountability, and collect unused study drug.
- Optional uptitration/sham titration if not yet on target dose, dispense study drug in accordance with dosing regimen for the 6 week interval until Visit 9 and instruct the patient on how to take the study drug.

- Patient to take the study drug (exact time of intake must be documented)
- Only in case of uptitration from dose step 3 to dose step 4, 2 h ± 15 min after study drug intake: Vital signs (BP and pulse rate). See Section [9.7.5](#).
- Schedule Visit 9 for Day 168±7
- For PK sampling at visit 9: Remind the patient to report the date and time of the last study drug intake the day before visit 9.
- Only for patients participating in the optional accelerometry substudy: activity tracking devices are planned to be handed out with instructions to use as specified in the accelerometry procedure manual.

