9.2.9 Visit 9 End of treatment – Day 168±7 (week 24)

Patients need to come to site without taking the morning dose of the study drug (this applies only for the study drug. All other medications shall be taken as scheduled).

The end of treatment visit should be scheduled at Day 168±7 also in case of premature discontinuation of study drug. All other visits and procedures should continue also if the study drug has been permanently discontinued.

- KCCQ, EQ-5D-5L, PGIC/S (see Section [9.4](#))
- Frailty assessment based on the Fried score
- Assessment of NYHA class
- Concomitant medications (see Section [8.1](#))
- Adverse events (see Section [9.6.1](#))
- Only for patients participating in the optional accelerometry substudy: Activity tracking devices are planned to be collected (see accelerometry manual).
- Physical examination
- Vital signs in sitting position (BP and pulse rate). See Section [9.7.5](#).
- 6MWT
- 12-lead ECG in patients not eligible for PK/QT assessment, see Section [9.7.4](#)
- Only in patients eligible for PK/QT assessment (all patients assessed as eligible based on the baseline ECG, see Section [9.7.4](#)) – ECG and PK sample should be collected time-matched, first ECG, subsequently PK sample:
 - 12-lead ECG (to be performed just before the PK sample is taken) to be taken prior to study drug intake (exact collection time must be documented)
 - Blood sample for PK prior to study drug intake (exact collection time to be documented)
- Central lab blood samples for NT-proBNP, hematology, clinical chemistry, coagulation and biomarkers [9.7.1](#) and blood sample for PK prior to study drug intake (exact collection time to be documented) in all patients, see Section [9.7.4](#)

- Drug accountability, incl. exact time of last dose intake the day before, and collect unused study drug
- Patient to take study drug (exact time of intake must be documented)
- Only in patients eligible for PK/QT assessment (all patients assessed as eligible based on the baseline ECG, see Section 9.7.4) – ECG and PK sample should be collected time-matched, first ECG, subsequently PK sample:
 - 12-lead ECG (to be performed just before the PK sample is taken) to be taken 1-2 h after study drug intake, exact collection times must be documented)
 - Blood sample for PK 1-2 h after study drug intake, exact collection time must be documented)

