 - 12-lead ECG in supine position, after resting for at least 10 min (to be performed just before the PK sample is taken) to be taken within the time interval of 3-6 h study drug intake (exact collection times must be documented)
 - Blood sample for PK within the time interval of 3-6 h after study drug intake (exact collection time must be documented)
- Schedule Follow-Up visit for Day 196±7

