9.6.1.3 Assessments and documentation of adverse events

The investigator has to record on the respective eCRF pages all adverse events occurring in the period between the signing of the informed consent and the end of the follow-up phase; after the end of the follow-up phase there is no requirement to actively collect AEs including deaths. The type of information that should be assessed and recorded by the investigator for each AE is listed in Section [9.6.1.2](#).

“Death” should not be recorded as an AE on the AE page. Instead, “death” is the outcome of underlying AE(s).

For all serious adverse events (SAEs) the sponsor has to carry out a separate assessment for expectedness, seriousness and causal relationship to study drug.

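### The follow-up AE incidence table in SAP 6.3.1 has no common window: about 23 days for completers, several times longer for early drug stoppers

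*SAP*

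**What the plan says.** SAP 6.3.1 counts an AE as treatment-emergent if it starts or worsens after first dose and "up to 5 calendar days after end of treatment with study medication". It then adds that the incidence of "AEs during the follow-up (more than 5 calendar days after end of treatment with study medication) will be tabulated". That category has a start but no end, and no denominator other than patients is mentioned.

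Protocol 9.6.1.3 has the investigator record "all adverse events occurring in the period between the signing of the informed consent and the end of the follow-up phase". For completers the calendar is clear. Treatment ends at Visit 9 (Protocol 9.2.8: "Schedule Visit 9 for Day 168±7") and the last AE visit is Visit 10 (Protocol 9.2.9: "Schedule Follow-Up visit for Day 196±7").

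Patients who stop drug early stay in the study. Protocol 6.3.1 says that for them "all visits and procedures, as outlined in the schedule of assessments, should be completed", and Protocol 9.2.9 that "All other visits and procedures should continue also if the study drug has been permanently discontinued". AEs are on that schedule (Table 9-1). SAP section 3 follows all patients to week 28. Early stoppers also have a safety visit about four weeks after last dose (Visit 12, Protocol 9.2.12).

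**The concern.** The table pools patients observed for very different lengths of time. The length is set by when the patient stops drug, which happens after randomization and can depend on tolerability. Safety and tolerability is a primary objective, and the protocol's benefit-risk section says the hypotension and syncope risks at 15 mg still need characterizing. Unequal stopping between arms is therefore plausible.

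If one arm has more early stops, its patients spend more time on average in the follow-up category. Their follow-up AE incidence is then expected to be higher even with no drug effect. A reader could take the excess for a withdrawal or carry-over effect.

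**Working it through.** **Inputs from the documents.** The window opens after day 5 post last dose (SAP 6.3.1). Visit 9 is nominally Day 168 and Visit 10 Day 196 (Protocol 9.2.8 and 9.2.9). As a check, 196 − 168 = 28 days, which agrees with the 28-day interval from last dose to Visit 12 in Protocol 9.2.12.

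**Window length** = (last day of AE collection) − (day of last dose) − 5.

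| Patient | AEs to Day 168 | AEs to Day 196 |
|---|---|---|
| Completer | not applicable | 196 − 168 − 5 = 23 days |
| Stops at Day 126 | 168 − 126 − 5 = 37 days | 196 − 126 − 5 = 65 days |
| Stops at Day 14 | 168 − 14 − 5 = 149 days | 196 − 14 − 5 = 177 days |

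For the Day 14 stop, the ratio to a completer is 149/23 = 6.5 or 177/23 = 7.7.

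**Illustration of size.** The documents give no AE hazard and no discontinuation rate for this trial, so these are assumptions:
- one constant hazard h of a first follow-up AE, equal in all arms and equal on and off drug, at 0.005 or 0.01 per day;
- stops spread evenly over Days 1 to 168 (a window that would be negative counts as zero);
- 8% versus 16% early stops.

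The probability of at least one follow-up AE is 1 − exp(−h × window). For completers this is 1 − exp(−0.005 × 23) = 10.86% or 1 − exp(−0.01 × 23) = 20.55%. For stoppers it is averaged over the stop days. Each arm is a mixture of the two groups, so the gap between arms is (difference in stop rates) × (stopper incidence − completer incidence).

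| h per day | AEs to | Stoppers | Completers | Gap, 8% vs 16% | Gap, 8% vs 10% |
|---|---|---|---|---|---|
| 0.005 | Day 168 | 30.51% | 10.86% | 0.08 × 19.65 = 1.6 points | 0.4 points |
| 0.005 | Day 196 | 39.55% | 10.86% | 0.08 × 28.69 = 2.3 points | 0.6 points |
| 0.01 | Day 168 | 48.92% | 20.55% | 0.08 × 28.37 = 2.3 points | 0.6 points |
| 0.01 | Day 196 | 61.33% | 20.55% | 0.08 × 40.78 = 3.3 points | 0.8 points |

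In the Day 196 rows the two arms would show 13.2% versus 15.5% (low hazard) and 23.8% versus 27.1% (high hazard). With a common 23-day window both arms would show 10.9% or 20.5%.

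**The case against.** The strongest objection is that AE collection in early stoppers may end well before week 28. Several places point that way:
- Visit 12 is titled their safety follow-up (Protocol 9.2.12).
- The footnote to SAP Table 4-1 ties their safety follow-up to last dose.
- Protocol 9.2.1 runs AE assessment to the follow-up visit.
- Footnote b of Table 9-1 and Protocol 9.2.10 expressly require only vital status at week 28 after discontinuation.
- Patients who cannot attend may be followed by phone, but only for the outcome events (Protocol 6.3.1).

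If collection ended at Visit 12, stoppers would also have 28 − 5 = 23 days and the gap would vanish. Part of this stands: week 28 is not settled as the end of AE collection. The Visit 12 reading does not displace the rest, however. The Table 4-1 footnote concerns KCCQ windows, and Protocol 6.3.1 and 9.2.9 keep visits and procedures, AEs included, running through Visit 9. SAP 6.3.1 itself sets no end.

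On size, the hazards and stop rates are assumed, and Protocol 3.2.1 reports low discontinuation in the earlier HFpEF study at doses up to 10 mg. The week-28 gaps for 8% versus 16% are below one standard error with 245 per arm: √(0.132×0.868/245 + 0.155×0.845/245) = 3.2 points, and likewise 3.9 points at the higher hazard. This stands as a limit on importance, but the shift is systematic and is not sampling noise.

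The table carries no test or decision rule. The overall AE summary, the Kaplan-Meier plots of time to end of treatment (SAP 6.1.6) and the listings with relative day would help a careful reader find the cause. None of them adjusts the table.

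**Conclusion.** The point holds as a minor one. As written, the follow-up AE table mixes 23-day windows with windows of 37 to 149 days (to week 24) or 65 to 177 days (to week 28). With equal hazards it is expected to favour the arm with fewer early stops. For 8% versus 16% stops the expected gap is about 1.6 to 3.3 points across both readings, and it is under 1 point when stop rates differ by 2 points. These sizes rest on the constant, equal hazard and the evenly spread stops assumed above.

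A reader might infer three stronger things that the documents do not support:
- That early stoppers are certainly observed for about 25 weeks. This needs AE collection to week 28 and a stop near Day 14, and the first is unclear.
- That an arm with more stops must show more follow-up AEs. This is true only in expectation under equal hazards, not for every observed count.
- That the trial's safety conclusion is biased. The primary safety variable is treatment-emergent AE incidence (Protocol 9.6), which ends 5 days after last dose and is not touched by this problem.

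**What to change.** In SAP 6.3.1:
1. State when AE collection ends for patients who stop drug early. Protocol 9.2.11 schedules Visit 12 at 30±7 days after last dose, while Protocol 9.2.12 and Table 9-1 say 28±7. These passages must be reconciled at the same time.
2. Limit the follow-up AE incidence table to day 6 through day 28 after last dose for all patients (28 − 5 = 23 days, the nominal completer window). Alternatively, report rates per patient-time.
3. Tabulate later off-drug AEs in early stoppers separately, with patient-time.

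A cap at day 35, the outer edge of the ±7-day visit window, would not equalise the groups. Stoppers on continuing visits would have 35 − 5 = 30 days against a nominal 23 in completers.

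The cost is a few sentences and one extra table, with no change to data collection. The downside is that late off-drug AEs move out of the main follow-up table.

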### **6.3.2 Adverse events of special safety interest**

For this trial, the following adverse events are considered of special interest:

- Symptomatic hypotension events (Bayer SMQ "Hypotension (Riociguat)" (code=SMQ\_1388)). Hypotension events will be categorized in symptomatic/asymptomatic as captured in the eCRF.
- Syncope (Bayer SMQ "Syncope Riociguat"( code=SMQ\_1389))

For each of the SMQs, the following tables will be provided: overall summary of TEAEs, incidences of patients with TEAEs, and with serious TEAEs grouped by SOC and PT.

A listing of all hypotension and syncope events will be provided, including date, relative day (to study medication), dose group, preferred term and phase of the study (pre-treatment, during treatment, post-treatment).

### **6.3.3 Further safety parameters**

#### **6.3.3.1 Laboratory parameters**

Summary statistics including changes from baseline will be calculated by treatment group and visit for all quantitative laboratory parameters. The summary statistics for troponin T and eGFR will also be provided by treatment group.

The number of patients with transitions from baseline with respect to reference range categories (low, normal, high) will be provided by treatment group and visit. In addition, the number of patients with treatment-emergent abnormal laboratory values above or below the normal range will be tabulated by treatment group and overall.

To assess acute renal failure, the number and incidence of patients with increase in serum creatinine  $>0.3$  mg/dL,  $>0.5$  mg/dL, and  $\geq \times 2$  from baseline, as well as the number and incidence of patients with decrease in eGFR  $>50\%$  or to  $<15$  mL/min/1.73m^2 will be presented by visit and treatment group.

The number and incidence of patients with ALT  $> 3 \times$  upper limit of normal (ULN), and total bilirubin  $> 2 \times$ ULN will be presented by visit and treatment group.

#### **6.3.3.2 Vital signs**

The absolute values and the changes from baseline values at each visit will be summarized by treatment group using descriptive statistics for systolic blood pressure (SBP), diastolic blood pressure (DBP), heart rate (HR).

The change in vital signs parameters from baseline to week 24 will be analyzed by two-sided two-sample t-tests comparing each individual vericiguat treatment group with the placebo treatment group at the 5% level in an explorative setting.

The number of patients with systolic blood pressure below 90 mmHg, based on the individual measurements rather than the mean value, will be displayed by visit and by treatment group. A frequency listing of all patients with systolic blood pressure below 90 mmHg post baseline will be provided.

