The main risk of vericiguat is hypotension. There was only a small increase in the rate of hypotension AEs at the starting dose of 2.5 mg (4.4% of patients in the first 2 weeks compared to 3.3% with placebo) in SOCRAVES-REDUCED, and these occurred only transiently upon initiation of vericiguat treatment in the majority of cases (26). In SOCRAVES-PRESERVED, treatment-emergent hypotension adverse events were similar in all arms including placebo. Therefore, by using the titration rules from SOCRAVES-PRESERVED, a safe uptitration to the target dose of 10 mg is expected in patients with HFpEF. In the absence of existing data with 15 mg vericiguat in patients with heart failure, the risks of hypotension and syncope with 15 mg vericiguat require further characterization. Based on previous experience from SOCRAVES-PRESERVED with doses up to 10 mg vericiguat, the risk of hypotension, syncope or any other intolerance is expected to be manageable and minimized through a non-forced titration also for the 15 mg dose.

Given the absence of life-saving drugs and the particular relevance of physical limitations in daily activities for patients with HFpEF, the potential for vericiguat to improve physical functioning based on exploratory data from SOCRAVES-PRESERVED appears to outweigh the manageable risks of hypotension and syncope observed with the 10 mg target dose. Therefore, before data for the 15 mg dose in patients with HFpEF will become available, there is equipoise with respect to the benefit-risk assessment for vericiguat 15 mg for the treatment of symptomatic HF in patients with chronic HFpEF, and we expect potential benefit in this indication.

4. Study objectives

The primary hypothesis in this trial is that the treatment with vericiguat 10 mg or 15 mg in patients with HFpEF improves the KCCQ PLS compared to placebo after 24 weeks of treatment.

Primary objectives:

- To evaluate the efficacy of vericiguat 10 mg in comparison to placebo on improving physical functioning from baseline to week 24.
- To evaluate the efficacy of vericiguat 15 mg in comparison to placebo on improving physical functioning from baseline to week 24.
- To evaluate the safety and tolerability of vericiguat.

Secondary objectives:

- To evaluate the efficacy of vericiguat 10 mg in comparison to placebo on improving distance traveled on a 6MWT from baseline to week 24.

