- f. 3 measurements, 2 min apart; measurements are taken prior to study drug intake. Additional measurement at 2h ± 15 min post study drug intake will be performed only at visit 2, and at visits 5-8 if dose is uptitrated from dose step 3 to step 4.
- g. Assessment of eligibility for PK/QT assessment.

Clinical Study Protocol
No. BAY 1021189 / 19334

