9.2.5 Visit 5 – Day 42±3 (week 6)

Patients need to come for this visit without taking the morning dose of the study drug (this applies only for the study drug. All others medications shall be taken as scheduled)

- Before titration / sham titration
 - KCCQ, EQ-5D-5L, PGIC/S (see Section [9.4](#))
 - Assessment of NYHA class
 - Concomitant medications (see Section [8.1](#))
 - Adverse events (see Section [9.6.1](#))
 - Physical examination
 - Vital signs (BP and pulse rate). See Section [9.7.5](#).
- Only in patients eligible for PK/QT assessment (all patients assessed as eligible based on the baseline ECG, see Section [9.7.4](#)) – ECG and PK sample should be collected time-matched, first ECG, subsequently PK sample:
 - 12-lead ECG (to be performed just before the PK sample is taken) prior to study drug intake (exact collection times must be documented)
 - Blood sample for PK prior to study drug intake (exact collection time to be documented)
 - Drug accountability, incl. exact time of last dose intake the day before, and collect unused study drug
- Titration/sham titration in accordance with dosing regimen in Section [7.4](#) and dispense study drug accordingly for the 2 week interval until Visit 6 and instruct the patient on how to take the study drug
- Patient to take first dose of titrated / sham titrated study drug (exact time of intake must be documented)
- Only in case of up titration from dose step 3 to dose step 4, at 2 h ± 15 min after study drug intake: Vital signs (BP and pulse rate). See Section [9.7.5](#).

- Only in patients eligible for PK/QT assessment (all patients assessed as eligible based on the baseline ECG, see Section 9.7.4) – ECG and PK sample should be collected time-matched, first ECG, subsequently PK sample:
 - 12-lead ECG (to be performed just before the PK sample is taken) to be taken 1-2 h after study drug intake, exact collection times must be documented)
 - Blood sample for PK 1-2 h after study drug intake (exact collection time must be documented)
 - 12-lead ECG (to be performed just before the PK sample is taken) to be taken within the time interval of 3-6 h study drug intake (exact collection times must be documented)
 - Blood sample for PK within the time interval of 3-6 h after study drug intake (exact collection time must be documented)
- Schedule Visit 6 for Day 56±3

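### The exploratory week-24 blood-pressure t-tests use no baseline or stratification covariates, and the SAP names no comparison of the 2-hour post-dose readings.

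*SAP*

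**What the plan says.** **The comparison.** SAP 6.3.3.2 says: "The change in vital signs parameters from baseline to week 24 will be analyzed by two-sided two-sample t-tests". Each vericiguat arm is compared with placebo, "at the 5% level in an explorative setting". No covariate is named.

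**Other vital-sign output in the same section.** "The absolute values and the changes from baseline values at each visit will be summarized by treatment group using descriptive statistics". Patients with SBP below 90 mmHg are also counted, "based on the individual measurements rather than the mean value, will be displayed by visit and by treatment group", and listed. Neither the count nor the listing is limited to pre-dose readings.

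**When readings are taken.** A footnote to Protocol Table 9-1 gives the routine measurement as "3 measurements, 2 min apart; measurements are taken prior to study drug intake". It continues: "Additional measurement at 2h ± 15 min post study drug intake will be performed only at visit 2, and at visits 5-8 if dose" moves from step 3 to step 4. Protocol 9.2.5 repeats this for Visit 5: "Only in case of up titration from dose step 3 to dose step 4". At Visit 9 (Protocol 9.2.9) patients arrive without having taken that morning's dose, and no post-dose vital signs are listed.

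**Why blood pressure matters here.** Protocol 3.3 names hypotension as the drug's main risk and says that "the risks of hypotension and syncope with 15 mg vericiguat require further characterization".

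**The concern.** Two things collected in this trial are left unused.

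First, baseline SBP, DBP and heart rate are available for essentially every patient, but the t-test only subtracts them. The same documents adjust for baseline elsewhere: the primary model in SAP 6.2.3.1 includes baseline PLS, region and heart rhythm, and the QTcF analysis in Protocol 10.6 is an ANCOVA on the baseline value. Blood pressure, which drives titration, gets the less precise method.

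Second, for a patient still on once-daily drug, the week-24 reading comes about a day after the previous dose, so the test addresses the effect at the end of the dosing interval. The protocol schedules triplicate readings 2 hours after dosing at two informative moments: the first dose, and the move to step 4, where the 15 mg arm goes from 10 to 15 mg while the 10 mg arm has a sham step. The SAP names no analysis of these readings and has no rule for keeping them apart from pre-dose values.

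The protocol itself raises the acute question. Protocol 3.2.1 reports orthostatic reactions and syncope in 3 of 4 healthy volunteers given 15 mg as a solution without titration, although single 15 mg doses as tablets were generally well tolerated in 14 volunteers. At stake are a moderately wider interval for the mean blood-pressure effect and the absence of a between-arm estimate of the early post-dose change.

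**Working it through.** **Inputs.** The plan has 245 patients per arm (Protocol 10.4). It states no SD, correlation, effect size or precision for blood pressure, so there is no stated figure on this point to reproduce. As a check on the arm size, 245 per arm with a 5-point difference, SD 21 and two-sided alpha 0.025 gives 65.3% power per comparison (stated: 65%) and 80.6% for at least one of the two (stated: 80%). The arm size is consistent with the plan. The SBP SDs and the baseline to week-24 correlation (rho) below are assumptions.

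**Formulas.** Let s1 and s2 be the baseline and week-24 SDs.

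- t-test on change: variance per patient = s1² + s2² − 2·rho·s1·s2
- ANCOVA: variance per patient = s2²·(1 − rho²)
- The difference between them is (s1 − rho·s2)², which is never negative.
- SE of an arm difference = √(variance) · √(2/n), and the 95% half-width = 1.96 · SE.

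**Equal SDs (s1 = s2).** The variance ratio is (1 + rho)/2, so the SE ratio is √((1 + rho)/2), whatever the SD and n. With SD 15 mmHg and n = 245:

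| rho | SE, t-test | SE, ANCOVA | SE ratio | Half-width, t-test | Half-width, ANCOVA |
|---|---|---|---|---|---|
| 0.3 | 1.60 | 1.29 | 0.81 | 3.14 | 2.53 |
| 0.5 | 1.36 | 1.17 | 0.87 | 2.66 | 2.30 |
| 0.7 | 1.05 | 0.97 | 0.92 | 2.06 | 1.90 |

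At rho 0.5, power for an illustrative 3 mmHg difference (two-sided 5%) rises from 60% to 72%. Over SDs of 12 to 18 mmHg and rho of 0.3 to 0.7, half-widths run from 1.65 to 3.77 mmHg for the t-test and from 1.52 to 3.04 mmHg for ANCOVA.

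**Smaller baseline SD.** Protocol 6.2 excludes SBP below 110 and at or above 160 mmHg at randomization, which can make s1 smaller than s2. Take s1 = 0.8 and s2 = 1 as an illustration, so Var(change) = 1.64 − 1.6·rho and Var(ANCOVA) = 1 − rho²:

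| rho | Var(change) | Var(ANCOVA) | Variance ratio | CI width ratio |
|---|---|---|---|---|
| 0.3 | 1.16 | 0.91 | 0.78 | 0.89 |
| 0.4 | 1.00 | 0.84 | 0.84 | 0.92 |
| 0.5 | 0.84 | 0.75 | 0.89 | 0.94 |
| 0.6 | 0.68 | 0.64 | 0.94 | 0.97 |

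Intervals are then about 3% to 11% narrower.

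**What the 2-hour readings can support.** No precision can be computed for them from the documents. By design:

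- *Visit 2:* due in everyone randomized and treated, before any titration decision. Both vericiguat arms receive 2.5 mg, so this reading informs the starting dose and not 15 mg.
- *First step 3 to step 4 move, 15 mg versus 10 mg:* planned doses are the same in both arms through step 3 (Protocol Table 7-3) and titration is blinded. Reaching the move should therefore not depend on which of the two arms a patient is in, and the contrast is close to randomized.
- *Same move, vericiguat versus placebo:* patients qualify on SBP criteria after weeks on drug or placebo. Selection may differ by arm, and the pre-dose value at that visit is itself affected by treatment.

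**The case against.** The strongest reply is that little is wrong. The tested outcome is already a change from baseline, so baseline is used, though not as a covariate. The test is labelled exploratory, vital signs are exploratory safety variables (Protocol 9.6), and the primary safety variable is the incidence of treatment-emergent adverse events. All of this stands, and it limits the point to efficiency and completeness.

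A reader might go further and infer any of the following. The documents support none of them.

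- *That limits on baseline SBP bias the test through regression to the mean.* The effect is expected equally in all randomized arms and cancels in the difference.
- *That hypotension is measured only before dosing.* The trial also has summaries at every visit, SBP counts and listings from individual readings, and tables and listings of symptomatic hypotension and syncope (SAP 6.3.2). Protocol 9.6.1.6 gives these events special DMC attention. Only the between-arm test is confined to the pre-dose week-24 value.
- *That the step-4 readings give a clean randomized comparison with placebo.* They are conditional on titration after randomization and spread over Visits 5 to 8. After an interruption, Protocol 7.4 allows re-titration, so a later move need not be a first 15 mg dose. Nor does a reading at uptitration stand in for a post-dose reading at week 24.

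Finally, PK/PD modelling that may relate safety parameters to concentrations belongs to a separate plan (Protocol 9.5), and PK analyses to a supplementary SAP (SAP section 2). The gap can be asserted for this SAP only.

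What remains is that a more precise analysis of the same data is available at almost no cost, and that scheduled 2-hour readings have no named analysis.

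**Conclusion.** The point holds as a modest improvement to an exploratory safety analysis. The t-test is valid. Baseline-adjusted ANCOVA would cut the standard error by 19%, 13% or 8% at rho 0.3, 0.5 or 0.7 with equal SDs, and by about 11% down to 3% at rho 0.3 to 0.6 if the baseline SD is 0.8 of the week-24 SD. These figures rest on assumed SDs and correlations and ignore any further gain from region and heart rhythm. No primary or secondary efficacy conclusion is affected.

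The second part rests on what the SAP leaves out: no comparison of the 2-hour readings is named, and nothing separates them from pre-dose values. Its size cannot be calculated. It merits attention because the protocol says the hypotension risk at 15 mg still needs characterizing.

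**What to change.** In SAP 6.3.3.2:

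1. Replace the t-tests with ANCOVA of week-24 change in SBP, DBP and heart rate on treatment, the pre-dose baseline value, region and heart rhythm. Report each difference from placebo with a 95% confidence interval.
2. Add an exploratory by-arm summary of 2-hour minus pre-dose change in SBP, DBP and heart rate, kept separate from the pre-dose by-visit values. At Visit 2 it covers all randomized and treated patients. At the first step 3 to step 4 move, make 15 mg versus 10 mg the main contrast, and label contrasts with placebo as conditional on reaching step 4.

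The word pre-dose in item 1 is needed. SAP 4.4.2 allows a baseline value on the randomization date, whereas SAP 4.1 requires one before first intake. The Visit 2 post-dose reading falls on the randomization date.

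The cost is SAP wording and minor extra programming; the readings are already scheduled. The limitation is that the step-4 summary covers only patients who are uptitrated, at varying visits (5 to 8), and the table should say so.
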